**Measurement-Based Transition Assistance (MBTA): Evaluating the Promise of a Web-Based Approach
to Promote Veterans' Support Seeking**

NCT05384171

2/27/2023

PROTOCOL

Overview. We conducted a pilot randomized controlled trial (RCT) that compared a prototype of MBTA to an active control condition. We collected data at baseline and at follow-up (three-months later). Participants in the active control condition did not receive the MBTA prototype until the follow-up assessment. Aims of the study were to evaluate the feasibility, acceptability, and preliminary effectiveness of the MBTA prototype in promoting Veterans' support-seeking in a sample of recently separated Veterans. Findings will be used to guide further modifications to MBTA, as this pilot study used a prototype of MBTA.

Sampling and Data Collection Method. We drew participants from a sampling frame of recently separated Veterans identified from the VA/DoD Identity Repository (VADIR). VADIR maintains automated files on all former military personnel with the necessary demographic and military background information to support the study. Inclusion criteria was: (1) having separated from active duty military service within the past year but not the past three months (for whom not enough time may have gone by to adequately assess readjustment challenges); (2) having a postal address in the U.S; (3) having access to the internet; and (4) having an honorable discharge from the military. We sent 500 initial invitations to potential participants, with the goal of obtaining a sample of 106 Veterans at baseline. Twenty-five invitations were undeliverable. We applied a modification of the Dillman mail survey. Specifically, a VA-approved vendor mailed an invitation letter to potential participants, along with information about how to complete the study at a secure website. Veterans were randomly assigned to the intervention or active control condition prior to mailing. Consistent with Dillman's recommendation for repeated contacts, a reminder letter was mailed, followed by a second reminder letter, and then a final reminder letter at the first (T1; baseline) and second (T2; three-month follow-up) wave of data collection. We sent a final mailing with a monetary incentive in the form of a \$25 Amazon gift card to Veterans who completed T1 (baseline) and increased the incentive to \$50 at T2 (three-month follow-up). The informed consent process was administered electronically. Informed consent elements were displayed on the screen along with a button that potential participants could select to consent to participate. Participants had the option to print the page and/or request a copy from the research team. A total of 43 Veterans elected to participate in this study and provided data at baseline.

Intervention Approach. This MBTA prototype required Veterans to complete a 6-8 minute online assessment that measured areas of unmet well-being and mental health needs, after which they received individualized feedback on areas of unmet need, along with tailored recommendations for relevant programs, services, and supports. Veterans assigned to the intervention condition completed MBTA at T1 (baseline); Veterans in the active control condition had the opportunity to complete MBTA at T2 (three-month follow-up). Drawing on recommendations from the feedback-informed treatment (FIT) literature, MBTA feedback was provided via a brief, easy-to-read infographic that included recommendations for relevant resources. The research team generated a list of vetted resources that were free to use and nationally available prior to study. Relevant context was provided to normalize readjustment challenges and feedback was framed in terms of response formats rather than peer comparisons. For example, within the domain of financial satisfaction Veterans received the feedback that they indicated not being satisfied with their finances on average, rather than that they are less satisfied than their peers. Because the report was provided online it was possible to present information in an easily digestible manner, for example, by limiting the amount of information presented on each page and providing feedback in tabs rather than a list-based format. We also offered Veterans the opportunity to download a printable version of the report for future use.

STATISTICAL ANALYSIS PLAN

For primary outcome #1, we generated frequency statistics. Primary analyses #2 and #3 involved evaluating the feasibility and acceptability of the tool (i.e., primary outcomes labeled as satisfaction of the tool) through qualitative data analysis of open-ended questions, specifically rapid content analysis. Unfortunately, the clinicaltrials.gov platform does not allow reporting on these types of analyses. Thus, the primary analyses that are presented here reflect only a subset of the analyses that were the focus of this study. We provided counts of themes generated from our qualitative data analysis.

For our secondary outcomes, specifically #1, #3, and #4, ANCOVA models were run. Baseline scores of the construct of interest and group status (intervention or active control) were entered as the independent variables and follow-up scores of the construct of interest was entered as the dependent variable. We also found significant age differences between the intervention and active control group, and differences among constructs of interest at baseline by age, so age was also entered in the models as a covariate. **Due to the small sample size of this pilot study, we encourage readers to focus on the magnitude of the effect that are provided in the results, specifically partial eta-squared values: $\eta^2 = 0.01$ indicate a small effect; $\eta^2 = 0.06$ indicate a medium effect; $\eta^2 = 0.14$ indicate a large effect. This study was not powered to detect statistically significant differences, although this information is presented due to clinicaltrial.gov requirements.**

For our secondary outcome #2, frequency statistics are reported. Participants who did not report challenges within a domain could not be categorized into a stage of change; therefore, our sample size for these analyses are smaller than the other secondary outcomes. Due to the smaller than expected sample size and because chi-square tests are sensitive to sample size, we elected to report descriptive information only for this outcome. We examined the subset of participants that reported challenges within a domain at baseline and then examined if they moved forward in their stages of change/were taking action to address these challenges by the three month-follow-up.

For our secondary outcome #5, we generated frequency statistics. Specifically, the number of participants that reported the MBTA prototype increased their awareness, encouraged them to improve their well-being, and if the Veteran reported using a resource/service. For the specific types of services used, frequency statistics were limited to the subset of Veterans that reported using a resource/service between baseline and follow-up.

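### Does calling the comparator an active control, when only delayed access to MBTA is described, call for a change to the plan?

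*Combined protocol and SAP*

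**What the plan says.** The Overview states that the trial "compared a prototype of MBTA to an active control condition", and adds: "Participants in the active control condition did not receive the MBTA prototype until the follow-up assessment". Intervention Approach says of the intervention arm: "Veterans assigned to the intervention condition completed MBTA at T1 (baseline". Of the other arm it says: "Veterans in the active control condition had the opportunity to complete MBTA at T2 (three-month follow-up". The same section sets out what MBTA contains. The prototype "required Veterans to complete a 6-8 minute online assessment that measured areas of unmet well-being and mental health needs", and this was followed by individual feedback, tailored recommendations drawn from a vetted resource list, and a report that could be downloaded.

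Sampling and Data Collection Method uses the same name for the comparator when it describes randomisation before mailing. It describes the letters, reminders and gift cards without distinguishing the arms.

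In the Statistical Analysis Plan the comparator enters a model for secondary outcomes #1, #3 and #4: "Baseline scores of the construct of interest and group status (intervention or active control) were entered as the independent variables", with age as a further covariate. Readers are asked to weigh partial eta-squared rather than significance, and are told that the study was not powered for significance testing.

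**The concern.** An active control normally receives something: a generic resource list, another tool, or a task matched for time and attention. Here the intervention is described in detail, while the comparator is described only by when it could use MBTA. That is how a wait-list arm is usually described.

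The distinction bears on interpretation. A difference from an arm given comparable information would point towards the individual feedback and tailoring. A difference from an arm given nothing for three months could also come from receiving any resource list, from added attention, or from controls putting off action because they expected the tool later. The Overview names preliminary effectiveness as an aim and says the findings will guide modification of MBTA, so a reader could credit the wrong component.

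There is also a timing question. Controls could use MBTA at the same contact that yields their follow-up outcome, so opening the tool before the outcome items were finished would contaminate that outcome.

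**Working it through.** No figure in the plan depends on this point, so there is none to reproduce. The check is a reading of every mention of the control arm, followed by a look at what the label feeds into.

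**What each section says about the control arm**

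| Section | Uses the label | States when controls got MBTA | States what else controls did or received |
|---|---|---|---|
| Overview | yes | yes: not before follow-up | no |
| Sampling and Data Collection Method | yes | no | only procedures not described by arm (letters, gift cards, two data waves) |
| Intervention Approach | yes | yes: opportunity at T2 | no |
| Statistical Analysis Plan | yes | no | no; baseline and follow-up scores are implied by the ANCOVA |

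The last column is empty of arm-specific content. Two readings therefore fit every sentence:

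1. Controls had outcome assessment only, then MBTA at T2.
2. Controls had some active task or material at T1, then MBTA at T2.

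The two timing sentences are true under both readings. They support the statement that the control condition is not described. They do not support the statement that nothing was provided.

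**What depends on the label**

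- *Secondary outcomes #1, #3 and #4.* The model is follow-up score = b0 + b1 × baseline score + b2 × group + b3 × age. The reported effect size is partial eta-squared = SS(group) / [SS(group) + SS(error)]. Both terms are computed from the scores, the ages and the two-level group indicator. Renaming a level leaves b2, both sums of squares and the ratio exactly as they were. Only the words used to interpret the ratio could change.
- *Secondary outcome #2.* The plan gives descriptive frequencies in participants with a challenge at baseline. It does not say that they are split by arm, although the abandoned chi-square tests may imply that a group comparison was once intended.
- *Primary outcomes.* These are frequencies and counts of qualitative themes on feasibility and acceptability. They use no between-group contrast.

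**Expectation effects.** Controls could defer action only if they knew MBTA was coming. The documents do not say what they were told; the consent text is not reproduced.

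**Order at T2.** No sentence gives the order of the outcome items and MBTA at the follow-up contact, and none implies that MBTA came first. The study is also reported in the past tense, with 43 Veterans providing baseline data, so a website setting could no longer be applied to it.

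**The case for a change.** The best argument for acting is that the plan's own caveats do not reach this point. Lack of power concerns precision, and a small pilot can still misdescribe what it compared. Because readers are told to rely on effect size instead of significance, the identity of the comparator carries more weight, and an effect size means little without it. Completing the same outcome measures as the other arm would not ordinarily earn the word active, and the documents never say that this is what the word means. Nor do they say whether the MBTA needs assessment is separate from the outcome measures. A clarification would cost a few words and no reanalysis.

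Much of this stands. The label is unsupported by anything written, the power caveat does not answer it, and a reader is entitled to know what controls received. It does not stand as a case for relabelling the arm as wait-list, because that would assert a fact the documents do not contain and could itself be wrong. Nor does it show a misleading claim: the delay is stated in the same paragraph as the label, the stated aim is preliminary effectiveness of a prototype, and no sentence attributes an effect to tailoring or claims benefit over an active comparator.

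**Conclusion.** No change to the plan is needed. The gap is one of description: the comparator is named but its content is not given. Its numerical size is zero, since no estimate, test, model or sample-size figure moves under either reading. Its interpretive reach is confirmed only for the three ANCOVA outcomes; the primary feasibility and acceptability results are untouched.

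Authors can fill the gap sensibly when they report the results, by stating what controls completed or received at T1 and between the two waves. If that was outcome assessment alone, the partial eta-squared values are to be read as MBTA against no MBTA for three months. The order of tasks at T2 can be reported in the same place.

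This rests on two assumptions: that controls' follow-up outcomes were collected before MBTA was opened to them, which the documents neither state nor contradict; and that the report will not claim superiority over active content unless such content was in fact delivered. If either failed, the interpretation of the three secondary contrasts would need to be revisited.

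### With at most 43 participants, the 'small' partial eta-squared label that readers are steered to does not separate an effect from noise (secondary outcomes #1, #3 and #4)

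*Combined protocol and SAP*

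**What the plan says.** The Statistical Analysis Plan fits an ANCOVA for each of secondary outcomes #1, #3 and #4. The independent variables are baseline score, group and age, and "follow-up scores of the construct of interest was entered as the dependent variable".

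It then advises the reader, giving the small sample as the reason: "we encourage readers to focus on the magnitude of the effect that are provided in the results, specifically partial eta-squared values". The measure named is partial eta-squared, with 0.01, 0.06 and 0.14 labelled small, medium and large. The text adds that the study was not powered for significance, "although this information is presented due to clinicaltrial.gov requirements". It mentions no confidence interval, sign or bias correction for the effect size.

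On numbers, Sampling and Data Collection Method states: "A total of 43 Veterans elected to participate in this study and provided data at baseline". The recruitment target appears in the same section: "with the goal of obtaining a sample of 106 Veterans at baseline". The number with follow-up data is not given.

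On purpose, the Overview states: "Aims of the study were to evaluate the feasibility, acceptability, and preliminary effectiveness of the MBTA prototype", and "Findings will be used to guide further modifications to MBTA".

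**The concern.** The small sample is offered as the reason to rely on partial eta-squared, yet a small sample is where the uncorrected measure is least reliable. Three properties matter.

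- It is a proportion of variance, so it is never negative. Chance differences between arms always register as a positive amount of effect, and the average under no effect lies above zero.
- It has no sign. A difference favouring the active control receives the same label as one of equal size favouring MBTA.
- Without an interval, a label gives no indication of how imprecise the value is.

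Preferring effect sizes to p-values in an underpowered pilot is reasonable. The difficulty lies in this particular measure, uncorrected and without an interval, being read against fixed labels. A reader who takes the advice could record a small benefit from a result that is typical of no effect. Preliminary effectiveness is one of the three aims, and the findings feed into changes to the tool.

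**Working it through.** **The plan's own figure.** The target of 106 comes with no alpha, power, effect size or dropout, so it cannot be reproduced. Nothing below depends on it.

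**Inputs.** From the documents: 43 participants at baseline (Sampling and Data Collection Method); model terms baseline score, group and age; cut-offs 0.01, 0.06 and 0.14 (Statistical Analysis Plan). Because the dependent variable is the follow-up score, the analysed N cannot exceed 43. Smaller follow-up numbers below are assumptions.

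**Step 1: error degrees of freedom.** Intercept plus three terms gives df = N − 4 = 43 − 4 = 39.

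**Step 2: distribution with no group effect.** For a term with one degree of freedom, partial eta-squared = F/(F + df). With no effect it follows Beta(1/2, df/2), with mean 1/(1 + df) = 1/40 = 0.025. The median is 0.012. Both exceed 0.01.

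**Step 3: chance of reaching each label with no effect.** P = P(F(1, df) ≥ c/(1 − c) × df) for cut-off c.

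| Analysed N | df | Null mean | P(≥ 0.01) | P(≥ 0.06) | P(≥ 0.14) |
|---|---|---|---|---|---|
| 43 (ceiling) | 39 | 0.025 | 0.534 | 0.123 | 0.016 |
| 34 (assumed) | 30 | 0.032 | 0.586 | 0.177 | 0.035 |
| 30 (assumed) | 26 | 0.037 | 0.613 | 0.209 | 0.050 |
| 26 (assumed) | 22 | 0.043 | 0.642 | 0.249 | 0.072 |
| 20 (assumed) | 16 | 0.059 | 0.693 | 0.327 | 0.126 |

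By symmetry of the t statistic, half of each probability favours MBTA and half favours control: at N = 43, 0.267, 0.061 and 0.008 in each direction. A simulation of 40,000 null trials at N = 43, with the arms differing in age by 0.7 SD, gave a mean of 0.025 and 53%, 12% and 1.7% at or above the three cut-offs. At the planned 106, P(≥ 0.01) would still be 0.31.

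**Step 4: chance of reaching a label when there is an effect (N = 43).** Noncentral F with λ = N × η²/(1 − η²).

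- True value 0.01: λ = 43 × 0.01/0.99 = 0.43. P(≥ 0.01) = 0.614, against 0.534 with no effect. P(≥ 0.06) = 0.200.
- True value 0.06: λ = 43 × 0.06/0.94 = 2.74. P(≥ 0.06) = 0.536, against 0.123 with no effect.

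**Step 5: what an observed value at each cut-off conveys (N = 43).** F = c/(1 − c) × 39. The interval comes from inverting the noncentral F, with limits λ/(λ + N). Partial epsilon-squared = 1 − (1 − η²) × (df + 1)/df; for 0.01 this is 1 − 0.99 × 40/39 = −0.015.

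| Observed | F | p | 95% CI | Partial epsilon-squared |
|---|---|---|---|---|
| 0.01 | 0.39 | 0.53 | 0 to 0.13 | −0.015 |
| 0.06 | 2.49 | 0.12 | 0 to 0.23 | 0.036 |
| 0.14 | 6.35 | 0.016 | 0.004 to 0.32 | 0.118 |

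At the 'small' cut-off the bias-corrected estimate is below zero.

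**The case against.** The strongest reply is that the sample size is at fault and not the measure. Given the error degrees of freedom, partial eta-squared, F and the two-sided p-value are one-to-one, and the adjusted difference with its interval rests on the same t statistic. No statistic from this ANCOVA could tell a true 0.01 from zero at N = 43. That is correct. It is also the reason not to direct readers to a label that presents 0.01 as an effect: an interval shows the imprecision and the label hides it.

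Second, the SAP openly says the trial is underpowered, presents significance results, and encourages rather than instructs. This is fair. But the underpowering caveat is attached to the significance tests and used to favour the effect sizes, with no matching caution on the effect sizes themselves.

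Third, the results are not in these documents. Arm means or intervals may be reported there, and no observed value need lie near 0.01. This stands as a limit on what can be said about actual harm; it does not supply what the plan omits.

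Fourth, the 'medium' label does carry information: 54% against 12% is a ratio of about 4.4, and passing a cut-off equal to the true value about half the time is expected. 'Large' is acceptable at N = 43. Both points stand, and the criticism belongs mainly to the 'small' label. The outcomes are also secondary, and no go/no-go rule depends on a label.

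**Conclusion.** The concern holds. At the best possible N of 43, the 'small' label is reached in 53% of trials with no effect and 61% with a true value of 0.01, so it does not separate the two. 'Medium' separates imperfectly: 12% with no effect, 20% at a true 0.01 and 54% at a true 0.06. 'Large' (1.6% with no effect) separates adequately at N = 43 but less well with follow-up loss, reaching 5% at an assumed N of 30. At every label the measure hides direction.

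These figures assume one model per construct, age and baseline score each entered as a single linear term, independent participants and normal errors. The no-effect results do not depend on the arm sizes, which are not given. The arithmetic is secure. The practical consequence depends on results not seen here and is confined to how secondary outcomes are reported and read. The point should be fixed.

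**What to change.** Change the reporting only, using the ANCOVA models already fitted.

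1. For each of outcomes #1, #3 and #4, make the adjusted mean difference (MBTA minus active control), its 95% CI and the number analysed the headline result.
2. If a variance-explained measure is kept, report bias-corrected partial epsilon-squared or omega-squared with a CI.
3. Remove the advice to focus on partial eta-squared and the fixed 0.01/0.06/0.14 labels.

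Possible wording: *For secondary outcomes #1, #3 and #4 we report the baseline- and age-adjusted mean difference (MBTA minus active control) with its 95% CI and the number analysed. Because the sample is small, these intervals are wide and should be read together with the estimates.*

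The cost is a revision of the SAP text and the results entry, with no new data or models. The effects will look smaller and visibly imprecise, which is an accurate picture of a trial of this size.
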